5.2 Provider Participant Characteristics

Survey respondent characteristics for participants who started the Site Characteristics will also be summarized by site and time period (Baseline Survey, Follow-up Survey 1, Follow-up Survey 2), and provider type (ED and community).

5.3 Focus Group Participant Characteristics

Focus group participants and their characteristics (age, sex, race, ethnicity, education level, employment status, job title and marital status) will be summarized by site for each wave (first month of IF, four to five months of IF, and near completion of IF period for the following categories: (1) patients, (2) providers and (3) all focus group participants combined.

6.0 STUDY INTERVENTION ADHERENCE

Several of the secondary implementation outcomes capture adherence to the study intervention (i.e., IF). See Section 7.6.1 for a list of all secondary implementation outcomes.

7.0 IMPLEMENTATION AND EFFECTIVENESS ANALYSIS

7.1 Definition of Primary Implementation Outcome Measure

The primary outcome is the rate of provision of ED-initiated BUP with referral for ongoing MAT. The rates of provision of ED-initiated BUP with referral for ongoing MAT will be based on:

1. Proportion of enrolled patients who receive ED-initiated BUP with referral for ongoing MAT or
2. Computed from ED data on the numbers of providers and their patients who received ED-initiated BUP with referral for ongoing MAT. As estimating a very low frequency outcome by sampling is not reliable, computation will be used if (1) results in zeros or small ratios. This entails reviewing existing ED records and counting the number of ED providers assigned to patients with OUD, and the number of patients who received ED-initiated BUP with referral for ongoing MAT during the study period.

Note that subsequent sections of this SAP indicate that there are statistical methodologies (a Bayesian approach and a ChangeToOne approach) that can be implemented to handle low frequency outcome. Thus, for the primary analysis the primary implementation outcome will be defined as in (1). A participant will be counted as having received ED-initiated BUP with referral for ongoing MAT if there is evidence that they were administered, prescribed, or provided BUP for take home administration. Further, there must also be evidence that the participant received a referral for opioid use disorder treatment. The primary implementation outcome measure will be scored from the ED Visit Review (EDR) form based on the following two questions:

- Were any of the following medications administered in the ED, prescribed at discharge, and/or given a take home dose?
- Did the patient receive a referral to opioid use disorder (OUD) treatment?

The outcome measure is calculated as an indicator that both of the following are true:

- BUP was administered in the ED, prescribed and/or provided for take home administration (i.e., ERBUPMED='1' or ERBUPRX='1' or ERBUPTH='1').
- Referral made for OUD treatment (i.e., EROPIREF='1')

If either of these criteria are met and the other missing, then the primary outcome measure will be missing. Since the data arise from the electronic health record, missing data should be exceedingly rare.

7.2 Analysis of the Primary Implementation Outcome Measure

For the primary implementation outcome measure, a Generalized Linear Mixed Model will be used to compare the rates of provision of ED-initiated BUP with referral for ongoing MAT between the baseline and IF evaluation periods. The model for the primary analysis will be used to compare the rates of ED-initiated BUP with referral for ongoing MAT between the IFEP and the BEP is:

$$\text{logit}(p_{si}) = \alpha + \beta t_{si} + \gamma f_{si} + r_s$$

where

- p_{si} is the probability of success of patient participant i at site s ,
- t_{si} is the calendar time of enrollment of patient participant i at site s ,
- f_{si} is the indicator of whether patient participant i at site s is in the BEP ($f_{si}=0$) or IFEP ($f_{si}=1$), and
- r_s is the random effect of site s , where $r_s \sim N(0, \sigma^2)$.

In this model the γ estimate represents the estimated difference in the logit of the probability of success and captures the effect of implementation facilitation. Note that calendar time is measured in days and defined in Section 3.3.6. The model will test a one-tailed hypothesis at the 0.05 level. The null and alternative hypotheses are:

$$H_0: \gamma \leq 0$$

$$H_a: \gamma > 0.$$

The following SAS code fragment estimates this model:

```
proc glimmix data = primout method = quad;
  class arm (ref="1") site;
  model z = arm time / dist = binomial link = logit solution;
  random intercept / subject = site;
  estimate "trt effect" arm 1 -1 / cl;
  lsmeans arm / cl ilink;
run;
```

where

- primout is the dataset containing the variables required for the primary outcome analyses;
- arm is 1 for the BEP and 2 for the IFEP;
- z is an indicator of the ED-initiated BUP (primary implementation outcome measure); and

- time is defined in Section 3.3.6.

The main focus for estimation is the estimated Risk Difference (RD) defined as the difference between IFEP and BEP success rates, ($p_{IFEP} - p_{EP}$) with its 95% credible interval (CI). The estimated RD and its 95% CI will be obtained using the Bayesian approach outlined in the protocol Appendix 19.0 and in this SAP. Below is the SAS code used for analyzing the primary implementation outcome for this model:

```
proc mcmc data = simmsimul nbi = 1000 nmc = 10000 thin = 2 seed = 159  
monitor =(alpha-gammacoeff gammacoeff_gt_0 p1 p2 pdiff) statistics = (summary  
intervals);  
  parms alpha-gammacoeff 0;  
  parms sigma2 1;  
  prior alpha-gammacoeff~normal(mean = 0, var = 1000);  
  prior sigma2~ igamma(shape = 0.001, scale = 0.001)  
  random b0 ~ normal(mean = 0, var = sigma2) subject = site;  
  array p[2];  
  p[treat+1] = logistic(alpha + beta * 22 + gammacoeff * treat);  
  pdiff = p2 - p1;  
  eta = alpha + beta * time + gammacoeff * treat + b0;  
  pi = logistic(eta);  
  model z ~ binomial(n = trials, p = pi);  
  gammacoeff_gt_0 = gammacoeff > 0;  
run;
```

where

- simmsimul is the analytic dataset (e.g., simulated dataset in power calculations);
- alpha is the intercept, beta is the coefficient β , gammacoeff is γ and sigma2 is the variance of the random effect of site from the logistic regression model above;
- time is defined in Section 3.3.6;
- treat is equal to '0' for the BEP and '1' for the IFEP;
- p1 is the proportion of success during the BEP;
- p2 is the proportion of successes in the IFEP; and
- pdiff is the risk difference.

The primary implementation outcome will be summarized by site and evaluation period with frequencies and percentages. Results of the Bayesian approach, that is the model specified above, will be presented tabularly with estimates and 95% credible intervals for the risk difference.

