12.8.1 Figure 2: ChangeToOne Power Analysis; Alternative Cases

We use LSMEANS to aid intuition concerning the precision to expect from these analyses. For the current application, the LSMEAN statement estimates, for each arm separately, the probability of success at the average time (roughly month 22). More specifically, this is a transform of a linear combination of the fixed effects. Random site effects are taken into account (via the variance of the estimated betas) when calculating confidence limits. Figure 3 shows the estimated probability, with 95% confidence intervals, for the baseline arm (black solid) and the IF arm (red dashed). The point estimates and confidence limits are averaged across the iterations of the simulation. Increasing ICC widens the confidence intervals considerably.

12.8.2 **Figure 3: ChangeToOne Confidence Intervals for p1, p2; Alternative Cases**

[figure not shown]

Figure 4 gives simulated test size (i.e. under the null hypothesis) at $\alpha = 0.05$, 1-tailed for the last 3 scenarios of Table 4, calculated on the basis of 10,000 iterations. A horizontal reference line marks 0.05, and the Y-axis scale goes from 0 to 0.1. Test sizes are tolerable, if not perfect.

12.8.3 **Figure 4: “ChangeToOne” test size; Null Cases**

[figure not shown]
[figure not shown]

Figure 5 gives LSMEAN estimates of the probabilities of success in the “null” scenarios of Table 4. As expected, the two arms agree as to success probabilities in this case. Again, increasing ICC widens the confidence intervals.

12.8.4 **Figure 5:** “ChangeToOne” Confidence Intervals, p1, p2; Null Cases

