3.3.6 Calendar Time

Calendar time for analysis is defined as the number of days since the site opened for enrollment in the baseline evaluation period. Below are the start and end dates for each site in each evaluation period. The start date is defined as the date the site was given access to the eClinical system to begin enrolling participants in the study for that particular evaluation period. The end date is defined as the last day the site was able to enroll participants in the EDC system for each evaluation period. Note that during the IFEP, enrollment was paused due to the COVID-19 public health measures put into place at two sites, Harborview Medical Center and University of Cincinnati. The days enrollment was paused will be considered as part of the primary analysis and several sensitivity analyses will be performed to account for this pause.

Site	Baseline Evaluation Period		IF Evaluation Period			
	Start Date	End Date	Start Date	Date Paused for COVID-19	Date Reopened for COVID-19	End Date
MA Johns Hopkins ED	4/10/2017	4/9/2018	10/9/2018	N/A	N/A	10/8/2019
NY Mount Sinai ED/Beth Israel	7/6/2017	7/5/2018	1/4/2019	N/A	N/A	1/5/2020
OV University of Cincinnati ED	10/9/2017	10/8/2018	4/8/2019	03/13/2020	6/10/2020	7/6/2020
PNW Harborview Medical Center ED	1/2/2018	1/1/2019	7/2/2019	03/3/2020	6/6/2020	10/4/2020

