7.2.1 ChangeToOne Policy versus the Bayesian Approach

Under the ChangeToOne policy, if a site-arm has "all zeros" data (that is, if all results for that site are zero in either the BEP or IFEP), one randomly chosen value of the zeros is changed into a one. By moving the data back from the edge of the outcome space the analysis method will be spared from having to deal with phenomena such as estimated variances of zero. Note that, under the alternative that the control arm has a lower success probability than the treated arm, this change will tend to move the arms closer together, and thus can be considered conservative.

Note that the protocol stated the ChangeToOne policy (see Section 12.8 of the protocol) would be used for the primary implementation outcome in the presence of any zero counts (i.e., no patient participants received ED-initiated BUP at a particular site in a particular evaluation period). A Bayesian approach (see Section 12.9 of the protocol), which has its own attractions and drawbacks, was also considered as a supportive analysis. Since the risk difference is of primary interest, the Bayesian approach will be used for estimating the risk differences, however the ChangeToOne policy will be used for the primary analysis to calculate a p-value based on the logistic regression model in Section 7.2. This logistic model assumes a linear effect of time on the log-odds scale, which corresponds to a time-varying risk difference scale. Thus the risk differences will be estimated at two time points, and may be calculated for other as well: (1) the last day for which one site was in the BEP and one site was in the IFEP (01/01/2019), and (2) the last day at which both enrolling sites were actively enrolling prior to the pause in enrollment due to the COVID-19 pandemic (03/02/2020).

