7.4 Analysis of Primary Effectiveness Outcome Measure

A mixed effects model will be used to compare the rates of patient engagement in formal addiction treatment for OUD on the 30th day post study enrollment between the baseline and IF evaluation periods. The model for the primary effectiveness will be used to compare the rates of engagement in formal addiction treatment for OUD on the 30th day post-index ED visit between the IFEP and BEP is:

$$\text{logit}(p_{si}) = \alpha + \beta t_{si} + \gamma f_{si} + r_s$$

where

- p_{si} is the probability of success of patient participant i at site s ,
- t_{si} is the calendar time of enrollment of patient participant i at site s ,
- f_{si} is the indicator of whether patient participant i at site s is in the BEP ($f_{si}=0$) or IFEP ($f_{si}=1$), and
- r_s is the random effect of site s , where $r_s \sim N(0, \sigma^2)$.

Note that calendar time is measured in days and defined in Section 3.3.6. In this model, γ captures the effect of implementation facilitation. The model will test a one-tailed hypothesis at the 0.05 level. The null and alternative hypotheses are:

$$H_0: \gamma \leq 0$$

$$H_a: \gamma > 0.$$

Similar to the implementation primary outcome, the main focus is the estimated Risk Difference (RD) defined as the difference between IF and Baseline engagement in treatment success rates, ($p_{IFEP} - p_{EP}$) with its 95% credible interval (CI). The estimated RD and its 95% CI will be obtained from the Bayesian approach as described in Section 7.3 for the primary effectiveness outcome. The SAS code will be analogous except p1 is now the proportion of patient participants engaged in formal addiction treatment for OUD on Study Day 30 during the BEP and p2 is the now the proportion during the IFEP.

The primary effectiveness outcome will be summarized by site and evaluation period with frequencies and percentages. Results of the Bayesian approach, that is the model specified above, will be presented tabularly with estimates and 95% credible intervals for the risk difference.

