16.1.3 Primary Implementation Outcome

**Table 13: Summary of Primary Implementation Outcome
by Evaluation Period**

Number	Baseline Evaluation Period (N=)	IF Evaluation Period (N=)	Total (N=)
Received ED-initiated BUP	N	N	N
Received referral for MAT	N	N	N
Received ED-initiated BUP with referral for ongoing MAT	N (XX.x%)	N (XX.x%)	N (XX.x%)

Table 14: Summary of Primary Implementation Outcome by Site and Evaluation Period

Number	Baseline Evaluation Period				IF Evaluation Period			
	MA Johns Hopkins ED (N=)	GNY Mount Sinai ED/Beth Israel (N=)	OV University of Cincinnati ED (N=)	PNW Harborview Med Center ED (N=)	MA Johns Hopkins ED (N=)	GNY Mount Sinai ED/Beth Israel (N=)	OV University of Cincinnati ED (N=)	PNW Harborview Med Center ED (N=)
Received ED-initiated BUP	N				N			
Received Referral for MAT	N				N			
Received ED-initiated BUP with Referral for Ongoing MAT	N (XX.x%)				N (XX.x%)			

Table 15: Analysis Results for Primary Implementation Outcome

GLMM		Bayesian Analysis		
Intervention Coefficient	p-value	Risk Difference Estimation Time Point	Risk Difference	95% Credible Interval
X.xx	x.xxx	Mid-point (day 632)	X.xx	X.xx; X.xx
		COVID-19 Pause (day 1423)	X.xx	X.xx; X.xx

**Table 16: Summary of Primary Implementation Outcome
by Sex and Evaluation Period**

Number	Baseline Evaluation Period		IF Evaluation Period	
	Male (N=)	Female (N=)	Male (N=)	Female (N=)
Received ED-initiated BUP	N		N	
Received Referral for MAT	N		N	
Received ED-initiated BUP with Referral for Ongoing MAT	N (XX.x%)		N (XX.x%)	

Table 17: Summary of Primary Implementation Outcome by Race and Evaluation Period

Number	Baseline Evaluation Period			IF Evaluation Period		
	White (N=)	Black/African American (N=)	Other (N=)	White (N=)	Black/African American(N=)	Other (N=)
Received ED-initiated BUP	N			N		
Received Referral for MAT	N			N		
Received ED-initiated BUP with Referral for Ongoing MAT	N (XX.x%)			N (XX.x%)		

**Table 18: Summary of Primary Implementation Outcome
by Ethnicity and Evaluation Period**

Number	Baseline Evaluation Period		IF Evaluation Period	
	Hispanic or Latino (N=)	Not Hispanic or Latino (N=)	Hispanic or Latino (N=)	Not Hispanic or Latino (N=)
Received ED-initiated BUP	N		N	
Received Referral for MAT	N		N	
Received ED-initiated BUP with Referral for Ongoing MAT	N (XX.x%)		N (XX.x%)	

**Table 19: Final Covariate Adjusted Model Analysis Results
for Primary Implementation Outcome**

Covariate ¹	N	Coefficient	95% Credible Interval
Study Phase			
BEP	N	[ref]	[ref]

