16.1.4 Primary Effectiveness Outcome

Table 22: Summary of Primary Effectiveness Outcome by Evaluation Period

Number	Baseline Evaluation Period (N=)	IF Evaluation Period (N=)
Self-report Treatment Engagement	N	N
Facility confirmed Treatment Engagement	N	N
Missing primary effectiveness outcome (i.e., to be imputed as non-engaged)	N	N
Engagement in formal addiction treatment for OUD at Day 30	N (XX.x%)	N (XX.x%)

Table 23: Summary of Primary Effectiveness Outcome by Site and Evaluation Period

Number	Baseline Evaluation Period				IF Evaluation Period			
	MA Johns Hopkins ED (N=)	GNY Mount Sinai ED/Beth Israel (N=)	OV University of Cincinnati ED (N=)	PNW Harborview Med Center ED (N=)	MA Johns Hopkins ED (N=)	GNY Mount Sinai ED/Beth Israel (N=)	OV University of Cincinnati ED (N=)	PNW Harborview Med Center ED (N=)
Self-report Treatment Engagement	N				N			
Facility confirmed Treatment Engagement	N				N			
Missing primary effectiveness outcome (i.e., to be imputed as non-engaged)	N				N			
Engagement in formal addiction treatment for OUD at Day 30	N (XX.x%)				N (XX.x%)			

Table 24: Analysis Results for Primary Effectiveness Outcome				
GLMM		Bayesian Analysis		
Intervention Effect Coefficient	p-value	Risk Difference Estimation Time Point	Risk Difference	95% Credible Interval
X.xx	x.XXX	Mid-point (time = 632)	X.xx	X.xx; X.xx
		COVID-19 Pause (time = 1423)	X.xx	X.xx; X.xx

Table 25: Summary of Primary Effectiveness Outcome by Sex and Evaluation Period

Number	Baseline Evaluation Period		IF Evaluation Period	
	Male (N=)	Female (N=)	Male (N=)	Female (N=)
Self-report Treatment Engagement	N		N	
Facility confirmed Treatment Engagement	N		N	
Missing primary effectiveness outcome (i.e., to be imputed as non-engaged)	N		N	
Engagement in formal addiction treatment for OUD at Day 30	N (XX.x%)		N (XX.x%)	

Table 26: Summary of Primary Effectiveness Outcome by Race and Evaluation Period

Number	Baseline Evaluation Period			IF Evaluation Period		
	White (N=)	Black/African American (N=)	Other (N=)	White (N=)	Black/African American (N=)	Other (N=)
Self-report Treatment Engagement	N			N		
Facility confirmed Treatment Engagement	N			N		
Missing primary effectiveness outcome (i.e., to be imputed as non-engaged)	N			N		
Engagement in formal addiction treatment for OUD at Day 30	N (XX.x%)			N (XX.x%)		

**Table 27: Summary of Primary Effectiveness Outcome
by Ethnicity and Evaluation Period**

Number	Baseline Evaluation Period		IF Evaluation Period	

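### The time-adjusted risk difference is coded at time = 22 (months, in a model measured in days), the shells date 2 March 2020 as day 1423 instead of day 1058, and SAP 3.3.6 starts the clock at each site's own opening

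*SAP*

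**What the plan says.** SAP 7.2 fits a logistic model with a linear effect of calendar time, an indicator for evaluation period and a random site intercept. On the unit it says: "Note that calendar time is measured in days and defined in Section 3.3.6". SAP 3.3.6 defines the variable: "Calendar time for analysis is defined as the number of days since the site opened for enrollment in the baseline evaluation period".

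SAP 7.2 makes the risk difference, with its 95% credible interval, the main target of estimation. The PROC MCMC code uses `beta * time` in the likelihood, but derives p1, p2 and their difference from "p[treat+1] = logistic(alpha + beta * 22 + gammacoeff * treat". SAP 7.4 carries this to the effectiveness outcome: "The SAS code will be analogous except p1 is now the proportion of patient participants engaged in formal addiction treatment for OUD".

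SAP 7.2.1 recognises that the risk difference varies with time under this model and names two estimation dates. The first is 1 January 2019. The second is "2) the last day at which both enrolling sites were actively enrolling prior to the pause in enrollment due to the COVID-19 pandemic (03/02/2020". The shells turn these into day numbers. The first is 632. The second appears as "COVID-19 Pause (day 1423" in Tables 15, 21 and 29, and as "COVID-19 Pause (time = 1423" in Table 24.

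The Revised SAP at the end of the document describes time as running from the start of the study. It then drops time and adopts a final model with fixed effects for site and evaluation period only.

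**The concern.** There are three faults in how the time-adjusted risk difference is specified.

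- **The constant 22.** It is a month value used in a model measured in days.
- **The label 1423.** It does not match the date it stands for.
- **The origin in 3.3.6.** Read as written, each site has its own clock, so one day number cannot stand for one calendar date at all four sites.

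Followed literally, the code would report a risk difference for a day before any IF evaluation data existed. If a programmer took the evaluation days from the shells instead, the mid-point rows would be right and the COVID-19 pause rows would extrapolate past the end of enrolment. Either way the estimate would carry the label of another date. This applies to both primary outcomes and to both COVID-19 sensitivity tables. The one-sided p-value for the period effect uses neither 22 nor 1423.

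**Working it through.** **Where 22 comes from.** Protocol 12.14.1 states that the simulations express time in integer months. Protocol 12.8.1 evaluates "the probability of success at the average time (roughly month 22"). The MCMC code in the protocol's Appendix 19.0 accordingly multiplies `beta1` by `month` in the likelihood and by 22 in the derived probabilities. SAP 7.2 changed `month` to `time` and left 22 in place. Twenty-two months is about 22 × 30.44 = 670 days, so even after conversion it would match neither date in 7.2.1.

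**Reproducing day 632.** The first site opened on 10 April 2017 (table in SAP 3.3.6). Counting that date as day 1, day = (date − 10 April 2017) + 1.

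| Date | Meaning | Day |
|---|---|---|
| 1 May 2017 | literal reading of 22 | 22 |
| 9 October 2018 | first IF evaluation day at any site | 548 |
| 1 January 2019 | first estimation date | 631 + 1 = 632, as in the shells |
| 2 March 2020 | second estimation date | 1057 + 1 = 1058 |
| 12 March 2020 | last day before the second of the two pauses | 1068 |
| 4 October 2020 | last enrolment day | 1274 |
| 2 March 2021 | literal reading of 1423 | 1423 |

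- Day 22 precedes the first IF evaluation day by 548 − 22 = 526 days.
- Day 1423 is 1423 − 1058 = 365 days late, and 1423 − 1274 = 149 days after enrolment ended.
- No site opening date, counted from 0 or from 1, turns 2 March 2020 into 1423. That would need an origin in April 2016, a year before any site opened.
- In the rows of Tables 21 and 29 restricted to pre-COVID data, 1423 lies 1423 − 1068 = 355 days beyond the last usable day.
- In the rows with the pause removed, the longer pause (3 March to 6 June 2020) is 95 days. The last compressed day is about 1274 − 95 = 1179, and 1423 lies about 244 days beyond it.

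**The origin in 3.3.6.** Elapsed days on each site's own clock, in the order of the 3.3.6 table:

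| Site opened | To 1 January 2019 | To 2 March 2020 | To last enrolment day |
|---|---|---|---|
| 10 April 2017 | 631 | 1057 | 911 |
| 6 July 2017 | 544 | 970 | 913 |
| 9 October 2017 | 449 | 875 | 1001 |
| 2 January 2018 | 364 | 790 | 1006 |

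On this clock neither estimation date has a single value, and no enrolment falls after elapsed day 1006. Day 632 therefore requires the study-wide origin.

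**How far the estimate could move.** The documents give no time slope, so this is an illustration. Take the protocol's planning rates (Tables 3 and 4), place them at day 632, and assume a slope b between −0.5 and +0.5 logits per year:

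RD(t) = expit(logit p2 + b(t − 632)/365.25) − expit(logit p1 + b(t − 632)/365.25)

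Worked case: 5% versus 25%, b = +0.5, t = 22. The shift is 0.5 × (22 − 632)/365.25 = −0.835 logits. The rates become 12.63% and 2.23%, a difference of 10.4 points.

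| Rates | b | Day 22 | Day 632 | Day 1058 | Day 1423 |
|---|---|---|---|---|---|
| 5% vs 25% | −0.5 | 32.6 | 20.0 | 12.8 | 8.4 |
| 5% vs 25% | +0.5 | 10.4 | 20.0 | 28.8 | 36.2 |
| 15% vs 25% | −0.5 | 14.5 | 10.0 | 6.7 | 4.5 |
| 15% vs 25% | +0.5 | 5.5 | 10.0 | 13.4 | 15.3 |
| 25% vs 40% | −0.5 | 17.1 | 15.0 | 11.4 | 8.3 |
| 25% vs 40% | +0.5 | 9.8 | 15.0 | 17.0 | 16.7 |

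Entries are percentage points. With b = 0 every row is constant across days.

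**The case against.** The strongest reply is that this analysis was superseded: the Revised SAP's final model for both primary outcomes has no time term, so no evaluation day enters it. That is correct and limits the scope. However, the Revised SAP does not withdraw 7.2, 7.4 or the four tables, so the time-adjusted analysis remains in the document.

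A second reply is that the code is a template. It names a simulated dataset, returns one risk difference and so cannot fill a two-row shell, while 7.2.1 states the intended dates. A silent run at 22 is therefore unlikely, and the documents do not show that one took place. But 7.2 presents the code as that used for the primary implementation outcome, and the constant contradicts 7.2.1.

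Third, 22 and 1423 cannot both drive the same estimate. This is fair: the two errors are alternatives for any given row, and the mid-point label of 632 is right.

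Fourth, 3.3.6 may simply be loosely worded, given its heading and the study-wide origin used elsewhere. That is plausible, and the remedy is then only to state the origin, but the text as it stands conflicts with the shells.

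Finally, the slopes are assumed, and the planning simulations had no time effect. The illustration shows sensitivity, not expected bias. At b = +0.5 the effectiveness difference moves only 0.3 points between days 1058 and 1423.

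**Conclusion.** The concern holds. The constant 22 is in the wrong unit, and 1423 should be 1058 on the count that gives 632 (1057 if the opening day is counted as 0; 1423 is wrong either way). The origin in 3.3.6 conflicts with the one the shells and the Revised SAP use.

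The errors affect the planned time-adjusted risk differences and credible intervals for both primary outcomes, and the COVID-19 sensitivity tables. Their numerical effect cannot be known without the fitted slope. It is nil for the point estimate at zero slope, and up to 12.6 points (32.6 against 20.0) in the illustrated range. The constant and the label do not change the p-value for the period effect. No size is claimed for the effect of the clock definition on that coefficient. The final time-free model is untouched. This should be fixed, but it does not undermine the final analysis.

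**What to change.** - In SAP 3.3.6, define time for all sites as (enrolment date − 10 April 2017) + 1, so that the first site's opening is day 1.
- In the 7.2 code, and in the effectiveness code under 7.4, replace 22 with the two stated time points, 632 and 1058, and output a risk difference at each.
- In Tables 15, 21, 24 and 29, change 1423 to 1058.
- Re-run any time-adjusted risk difference already produced with 22 or 1423.
- Add a note in 7.2 and 7.4 that the Revised SAP's final model has no time term and needs no evaluation day.

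The cost is one definition, the evaluation constant in the code, four shell labels, a short note, and a re-run of any affected output. No new data or patients are needed.

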Figures B6-B7 shows Bayes estimates for p_1 , p_2 , and $p_1 - p_2$. The average credibility intervals for p_1 and p_2 are somewhat wider than corresponding confidence intervals. The reason for this is unclear. Although the treatment effect is an odds ratio. i.e., $p_2(1 - p_1)/[p_1(1 - p_2)]$ in both approaches, an attractive aspect of the Bayes MCMC method is that it is easy to get the posterior distribution of the simple treatment difference, as shown $p_2 - p_1$ in Figure B7. The credibility interval for $p_1 - p_2$ seems less sensitive to ICC than other interval estimates investigated.

[figure not shown]

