Evaluation of the distributional properties of the time variable data indicated that this variable, originally included as one of the explanatory factors in the analytical model, overlaps 96% with the intervention/treatment factor in the study. Including two highly overlapping variables in the analytical model can create a computational, statistical, and mathematical error. Collinearity, or high association between two explanatory variables means that the collinear variables contain the same information about the dependent variable, and that these only nominally different measures actually quantify the same

phenomenon or information. In CTN-0069, the variables “time” and “arm” are highly redundant. The best and most statistically robust analytical models are called “low noise” models in which the predictor variables each correlate highly with the outcome variable but correlate with each other at most only minimally. Collinearity and redundancy may lead to a failure to reject a false null hypothesis of no intervention effect. Consequently, the “time” variable was removed from the adjusted computational model.

Site. Additionally, the four geographically diverse study sites were purposefully selected to represent different clinical contexts and different patient populations. Conceptually, these EDs cannot be considered as a random sample of all EDs in the US, and probabilistically, no four values selected from a large population can be considered to represent randomness, even if they are drawn by chance. Consequently, site was included in the primary analytic models as a fixed effect, and not a random one in order to provide additional information on between site differences. The study results demonstrated not only statistical difference effects between the sites, but also substantial, large, important, and informative site differences.

Thus, the final analytic model for both the primary implementation and effectiveness outcomes was a logistic regression model with fixed effects for site and evaluation period.

Site Differences for Primary Effectiveness Outcome

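### The coded risk difference is for a hypothetical ED with zero site effect, not for the patients enrolled at the four EDs, and at a low baseline rate its credible interval is too wide for that target

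*SAP*

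**What the plan says.** SAP 7.2 states the target: "The main focus for estimation is the estimated Risk Difference (RD) defined as the difference between IFEP and BEP success rates", with a 95% credible interval. SAP 7.1 bases the outcome on the proportion of enrolled patients, and the key under the code describes the baseline quantity in the same terms: "p1 is the proportion of success during the BEP".

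The code fits "eta = alpha + beta * time + gammacoeff * treat + b0", with "random b0 ~ normal(mean = 0, var = sigma2) subject = site" and "prior sigma2~ igamma(shape = 0.001, scale = 0.001". The two rates, and hence their difference, then come from "p[treat+1] = logistic(alpha + beta * 22 + gammacoeff * treat", which has no site term. The code in the protocol's Bayesian appendix (19.0) has the same structure.

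SAP 7.4 says that the effectiveness code is analogous. The result fills the table shells for both primary outcomes and their COVID-19 sensitivity analyses (Tables 15, 21, 24 and 29).

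The Revised SAP at the end of the document removes time and makes site a fixed effect, on the ground that "these EDs cannot be considered as a random sample of all EDs in the US". It does not say how a risk difference is to be obtained from that model.

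**The concern.** The logistic function is not linear. The difference in probability at a site effect of zero is therefore neither the average difference over the four EDs nor the average over a distribution of EDs. Nothing in either document names a zero-effect ED as the target.

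The interval is affected as well. To place a zero-effect ED, the model must locate the centre of a distribution from four sites under a diffuse variance prior. That uncertainty enters the interval although it says little about how success rates changed at the EDs actually observed. The risk difference is the figure that readers will take from the trial, so its meaning and its precision are both at stake.

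**Working it through.** **Inputs.**
- Model and priors: SAP 7.2 (coefficients normal with variance 1000, site variance inverse-gamma 0.001/0.001).
- Size and rates: four sites with 120 patients per period and the Table 4 rates (Protocol 12.6).
- ICC: power is summarised for values below 0.3 (Protocol 12.9.1; SAP 10.2). SAP 10.0 expects a low baseline rate together with a large ICC.
- Evaluation dates: SAP 7.2.1. Counting 10 April 2017 as day 1, 1 January 2019 is day 632 and 2 March 2020 is day 1058. The table shells print 1423 for the second date; I used the date. The constant 22 in the quoted line is a separate matter.
- Assumption: normal site effects on the logit scale. The documents cite a data generator without describing it.

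**The plan's own figures.** On the protocol timeline the mean enrolment month is 22.0, as Protocol 12.8.1 says (roughly 22). Simulated Bayesian power was 0.95–0.99 in the two optimistic scenarios at ICC 0–0.3, against a stated value above 0.8. It was 0.46–0.68 in the other two, which the plan describes only as lower.

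**Target.** Let p(b) = logistic(m + b) with b ~ N(0, s²), and choose m so that the mean of p(b) equals the Table 4 rate. Take the ICC as Var[p(b)] / [p̄(1 − p̄)], averaged over the two periods. At ICC 0.3:
- 5% versus 25% (s = 2.03): the zero-effect ED has rates of 1.1% and 14.2%. Its risk difference is 0.142 − 0.011 = 0.131, against 0.25 − 0.05 = 0.20 on average.
- 25% versus 50% (s = 1.60): the rates are 17.1% and 50.0%. The risk difference is 0.329, against 0.25 on average.

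The discrepancy changes direction between scenarios.

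**Width.** From the same posterior draws, two quantities were computed: (a) the coded difference at b0 = 0, and (b) the difference averaged over the four sites with their own b0. Results for 5% versus 25% on the actual site calendar, 60 data sets per cell, mean 95% interval width:

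| ICC (site SD) | Day 632: (a) / (b) | Ratio | Day 1058: (a) / (b) | Ratio |
|---|---|---|---|---|
| 0.05 (0.67) | 0.288 / 0.191 | 1.5 | 0.233 / 0.106 | 2.2 |
| 0.10 (0.99) | 0.364 / 0.196 | 1.9 | 0.322 / 0.113 | 2.9 |
| 0.30 (2.03) | 0.523 / 0.173 | 3.0 | 0.491 / 0.111 | 4.4 |

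Separate runs on the planned schedule, with site SD fixed at 0.5 and 1.0 logits, gave 0.268 / 0.208 = 1.3 and 0.357 / 0.216 = 1.65 on 1 January 2019. On 2 March 2020 the ratios were about 1.7 and 2.4.

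**Where the excess is small.** For 25% versus 40% it was about 5% to 25% at those two SDs. At month 22 on the protocol timeline, the scenarios with higher rates gave ratios of 1.0–1.2 at ICC up to 0.1 and 1.4–1.6 at ICC 0.3. At ICC 0, 5% versus 25% gave 1.07.

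**Point estimate.** The mean absolute difference between (a) and (b) at day 632 was 0.003, 0.008 and 0.038 at ICC 0.05, 0.10 and 0.30 (5% versus 25%).

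**Coverage of the four-site difference.** In the table's runs, (a) covered it in 98–100% of data sets and (b) in 95–98% at day 632. At day 1058, (b) covered 92%, 98% and 87%. With 60 data sets the Monte Carlo standard error near 95% is √(0.95 × 0.05 / 60) = 0.028. The 87%, at ICC 0.3, is therefore low, and the 4.4 in that cell may overstate the excess.

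**The case against.** The strongest reply is that the criticised line belongs to an abandoned model. The Revised SAP's final model has no random site effect and no variance prior. That is correct, and it limits the point about the code to SAP 7.2, SAP 7.4 and the appendices. It does not settle the estimate: a logistic model with fixed sites gives a different risk difference at each site until someone says how to average them, and the Revised SAP does not.

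A second reply is that the difference at a typical site is a legitimate quantity, and that the width is right for it. This also stands in part: the interval is too wide only relative to the four-site difference. But the SAP describes its target as success rates in the two periods and never mentions a typical site. If the target were instead a population of EDs, the coded interval would still be too wide: 0.523 against 0.312 for the population average (ICC 0.3, day 632), a ratio of 1.7.

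Third, the consequences are bounded. The p-value comes from γ, the error in the interval is conservative, and observed rates by site and period are tabulated anyway. All of this is accepted.

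Two stronger readings are tempting but unsupported:
- A reader might think that the omitted site term explains why the appendix finds Bayesian intervals for the two rates wider than the frequentist ones, where it says "The reason for this is unclear". It cannot. Protocol 12.8.1 describes the frequentist LSMEANS as a transform of fixed effects only, so both sides of that comparison omit the site effect.
- A reader might also infer that the Revised SAP makes the excess worse by dropping time. Keeping the random intercept while dropping time is a model that neither document specifies; the Revised SAP removed both together.

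**Conclusion.** The point holds for the meaning and precision of the main estimate, not for the hypothesis test. As coded, the risk difference refers to a zero-effect ED. In the situation that the plan itself calls likely, its interval is materially wider than the data on the four EDs require: about 1.3 to 2.4 times at site SDs of 0.5 to 1.0 logits, and about 3 to 4.4 times at ICC 0.3. At 25% versus 40% the loss is modest. The change is worth making, but it does not threaten the trial's conclusion on the primary hypothesis.

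The ratios rest on assumed normal site effects, equal enrolment of 240 per site and no time trend in the generated data. The two sets of runs agree in direction but not exactly in size. The omission of the site term is certain from the code; its size depends on between-site variation that the plan does not fix.

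**What to change.** In SAP 7.2 and 7.4, at each posterior draw and for each period f (0 or 1), compute

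p(f) = Σ w(s) × logistic(α + β·t + γ·f + b0(s)), summed over the four sites,

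and report p(1) − p(0). Set w(s) to each site's share of total enrolment over both periods and use the same weights for both periods, so that a shift in site mix cannot enter the difference. Show equal weights as a sensitivity analysis. SAP 11.0 reports very low baseline recruitment at one site and two sites above target, so the choice may matter. The Revised SAP already reports results, so the weights can no longer be called prespecified. Enrolment shares do not depend on outcomes, and the report should state when they were chosen.

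Under the Revised SAP's model, replace α + b0(s) with the fixed coefficient for site s, omit the time term, and standardise in the same way. State that the result applies to the four EDs studied.

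The cost is a few lines of code and one sentence in each section. No new data are needed and the test is unchanged. The price is that the estimate makes no claim about other EDs, which is already the Revised SAP's position.
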